#### Procedures for Reporting any Deviation(s) from the Original Statistical Plan

Deviations from the original statistical plan are unlikely. However, should they occur, then approval for such changes will be sought from the ERC and these changes will be reported in the final report and papers.

## 4.9. Data/Sample storage and disposal

Data will be entered and saved in a dedicated computer with password protection. Hard copy of data will be stored in a secure place and accessible only to investigators. Samples of blood of volunteers after testing would be stored in a secure facility, under suitable conditions during storage. Samples will be disposed of immediately after completion of the study publication. No samples would be used for any analysis other than the ones stipulated in the study proposal.

#### 4.10. Dissemination of results

Results will be disseminated widely through peer reviewed scientific communications and publications in indexed journals. Dissemination and presentation of results will be done irrespective of the positive or negative nature of results.

#### Sharing data with study participant

The results of this study will be shared with the volunteer participants after completion of the study, by the investigators at an open forum, without compromising confidentiality or identity of the participant.

28.02.2025

## 5. Intervention, Monitoring of compliance to treatment

Caffeine tablets and placebo tablets required for the trial would be sourced from Nutricost, a U.S.-based company that specializes in high-quality dietary supplements. Nutricost products are manufactured in GMP-compliant facilities and undergo third-party testing to ensure purity and consistency. The caffeine tablets specifically contain caffeine anhydrous, a dehydrated form of caffeine that provides a standardized and effective dosage and placebo are manufactured using starch ensuring that it is inert and does not affect the study's outcomes.

The study groups will receive one bottle on the day of allocation, and it will contain either caffeine tablets or placebo required for a month. The test group will receive the caffeine tablet while the control group will receive the placebo .Tablet bottles will be issued to participants according to their random number mentioned in the Case Report Form (CRF).

Patients will be asked to take the medication every day after dinner. Recommended dose and directions for use will be given verbally when dispensing the tablet pack, and written instructions will be clearly mentioned on the label of the bottle in Sinhala, Tamil and English. The patients will be asked to take the tablets home. At each monthly visit, the participants will be asked to bring tablet bottles with balance tablets, to count at the monthly visit to assess compliance. The required tablets for next month will be issued during this visit.

Participants who have < 80% compliance will be re-educated on the importance of daily administration of investigational product, as much as possible: with the overall aim to maintain  $\ge$  80% compliance over the study period.

## 5.1. Lifestyle modification and standard care during the study period

There is currently no approved pharmacological treatment which can reverse NAFLD or control disease progression. Hence current treatment strategies are focused on lifestyle modifications. All patients in the two groups will receive standard diet modification and exercise and physical activity recommendations according to Clinical Practice Guidelines developed by Sri Lanka College of

28.02.2025

Endocrinologists, Sri Lanka society of Gastroenterology, 2019. However, management of comorbid conditions such as diabetes and hypertension will be as per routine hospital practice based on guidelines. If patients are already on pharmacological treatment for NAFLD, such patients will not be recruited to study.

Before recruitment all participants will be made aware of the required lifestyle modification during the study period as per standard management schedule.

#### **5.2.** Dietary measurements

All patients will be instructed on a balanced diet, including decreased intake of saturated and trans fats and increased intake of fiber. In overweight patients, dietary intervention will focus on a calorie restricted diet, attained over a 6-month period. The calorie-restricted diets will be planned to create a deficit of 500- 1000 kcal/day and will be individualized for each study subject. A culturally validated Food Frequency Questionnaire (FFQ) will be used to obtain habitual intake of calories, macronutrients and micronutrients. This will be assessed monthly to monitor dietary measurements of participants.

Medical RA will meet individual patients for counselling on dietary intervention. All patients are asked to maintain food logs and ask to bring it on follow up visits and food logs will be reviewed monthly, and diet plans will be adjusted as needed.

Dietary measurements will be monitored at the baseline and during each follow up monthly visits.

## 5.3. Physical activity

Physical activity will be evaluated by using the International Physical Activity Questionnaire (IPAQ) short Version, which is a user-friendly measurement tool that comprises of 7 questions that considers the level of physical activity in the past 7 days. This will be assessed monthly to monitor the physical activity of participants. Moderate-intensity exercise for 30 – 60 minutes (ex: 30 minutes of walking/day) on 3–5 days per week is recommended during the study period.

28.02.2025

### 5.4. Alcohol consumption

Intake of alcohol is not recommended and if consumed should not exceed the limit mentioned in exclusion criteria 20 g/day for women and 30g/day for men  $\geq 2$  units alcohol/day for women and  $\geq 3$  units for men during the study period.

The Alcohol Use Disorders Identification Test (AUDIT) is a 10-item screening tool developed by the World Health Organization (WHO) to assess alcohol consumption, drinking behaviors, and alcohol-related problems. This is validated questionnaire and Sinhala and Tamil translations are freely available to use. Frequency of alcohol consumption will be assessed monthly using AUDIT questionnaire in all patients.

#### 5.5. Follow up assessment

The recruited patients will be advised to come for monthly assessments and will be asked to attend the nearest hospital, if they develop any complications and inform the study team of such incidence.

The degree of adherence to prescribed lifestyle changes and diet will be recorded at the baseline and monthly follow-up visits. Physical activity and alcohol consumption will also be monitored at the baseline and monthly follow-up visits.

Anthropometric measurements, physical examination and vital sign measurements (BP, HR, RR etc..) will be monitored at the baseline and each monthly visit. Details on concomitant medications will be recorded in monthly visits.

Liver profile, Lipid profile, Full blood count, Serum creatinine, fasting blood glucose, HbA1c, serum insulin, serum electrolytes and urine analysis and serum insulin will be investigated at the baseline, at 3 months and 6 months.

Fibro scan will be done at the baseline and after 6 months at the completion of the study.

The details of items which will be measured on every visit are described in Table 2.

Table 2: Summary of follow up

	Enrolment	Allocation 1	Subsequent visits							
TIME POINT		0	1 st	2 nd	3 rd	4 th	5 th	6 th		
			mont	mont	month	mont	month	mont		
			h	h		h		h		
ENROLMENT										
Eligibility screen	×									
Informed consent	×									
Allocation		×								
INTERVENTIO										
NS										
caffeine or		×	×	×	×	×	×			
placebo										
ASSESSMENTS										
Medical history	×	×	×	×	×	×	×	×		
taking										
AUDIT	×	×	×	×	×	×	×	×		
FFQ and IPAQ	×	×	×	×	×	×	×	×		

Height, weight			×	×	×	×	×	×
and waist								
circumference								
Blood pressure	×	×	×	×	×	×	×	×
Physical examination 	×	×	×	×	×	×	×	×
USS scan	×							
Fibro scan		×						×
FBG	×	×			×			×
Fasting serum insulin		×			×			×
HCG only female	×							
Serum HbA1c		×			×			×
Lipid profile	×	×			×			×
Liver enzymes	×	×			×			×
Total bilirubin	×				×			×
Serum creatinine		×			×			×
Serum electrolytes		×			×			×

FBC	×		×		×
UFR	×		×		×

28.02.2025

## 6. Ethics approval and related issues

Ethics approval will be obtained from the Ethics review committee, university of Kelaniya, to conduct the study, and the clinical study will be registered at the Sri Lanka Clinical Trials Registry. The trial will be conducted in compliance with the Good Clinical Practice guidelines

## 6.1. Benefits and the risks of the study

#### **Benefits**

The study will provide high quality clinical evidence on the effects of caffeine supplementation on hepatic steatosis and fibrosis. It would help establish a causal relationship and propose an alternative or complementary strategy to diet and exercise in the treatment of NAFLD.

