#### 4.3.2. Exclusion Criteria

- History of unsafe alcohol consumption
- Other liver disease (chronic viral/autoimmune/hereditary)
- Use of steatogenic medications
- History of drug dependence
- Body mass index (BMI) ≥35 kg/m2

28.02.2025

- A restrictive diet or weight change  $\geq 5$  kg during the 3 months prior to study
- Pregnancy or lactation
- Patients with sensitivity to caffeine intake
- Patients with symptomatic ischaemic heart disease, arrythmia's
- Any condition that, in the opinion of the clinician, would contraindicate the patient's participation.

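### Both arms receive the same diet and exercise programme, so the trial can estimate only what caffeine adds to it; the word 'alternative' in Section 6.1 has no arm behind it

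*Protocol*

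**What the plan says.** The Benefits paragraph of Section 6.1 expects the trial to establish causality and to "propose an alternative or complementary strategy to diet and exercise in the treatment of NAFLD".

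The background care is set out in Section 5:

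- Section 5.1: "All patients in the two groups will receive standard diet modification and exercise and physical activity recommendations". The same section adds: "Before recruitment all participants will be made aware of the required lifestyle modification during the study period".
- Section 5.2: "All patients will be instructed on a balanced diet". A further step applies to some participants only: "In overweight patients, dietary intervention will focus on a calorie restricted diet, attained over a 6-month period". The plan is to "create a deficit of 500- 1000 kcal/day and will be individualized for each study subject".
- Section 5.3 recommends moderate exercise on 3 to 5 days per week.

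Sections 4.1 and 5 describe two parallel groups, one on caffeine tablets and one on placebo tablets. Section 4.8 compares mean change in CAP and LSM from baseline to 6 months between these two groups by an independent t test or a Mann-Whitney test. It also lists repeated measures ANOVA. It names no covariate.

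**The concern.** The Benefits sentence offers two roles for caffeine: in place of diet and exercise, or alongside them. The design can speak to the second only. The sections that define the question (hypothesis, primary objective, justification) do not mention the lifestyle background, and Section 3 aims to show that coffee works as a dietary means of managing the disease and to inform guidelines. A positive result could then be reported as evidence for caffeine on its own, which the trial does not test.

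A second, smaller matter follows from the same background care. The diet differs within the trial by a baseline feature, overweight status. That feature is therefore a plausible predictor of CAP and LSM change, and the stated comparison ignores it.

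**Working it through.** **1. What the arms can estimate.** Write L for the lifestyle programme, C for caffeine and P for placebo.

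| Combination | In the trial? |
|---|---|
| L + C | yes (test group) |
| L + P | yes (control group) |
| C without L | no |
| neither | no |

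The randomised contrast is (L + C) − (L + P), the effect of caffeine added to lifestyle care. To call caffeine an alternative to diet and exercise, one needs C without L compared with L, or at the least C without L compared with neither. Neither comparison can be formed.

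**2. The sample size belongs to the same contrast.** Section 4.4 gives a standard deviation of 5, a difference of 3, two-sided 0.05, 80% power and 20% dropout. The usual two-sample formula gives

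n = 2 × 5² × (1.96 + 0.84)² / 3² = 2 × 25 × 7.84 / 9 = 43.6, so 44 per group; 44 / (1 − 0.20) = 55.

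This reproduces the stated 55 per group (110 in total). The formula as printed, without the factor 2 and with the difference not squared, gives 25 × 7.84 / 3 = 65.3 before dropout. That is a separate matter and does not affect this point. The calculation is for superiority between two groups that share the same background. It has no third arm and no margin against diet and exercise.

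**3. Claim and design side by side.** Section 6.1 names both roles. Sections 5.1 to 5.3 make lifestyle care common to both arms, which fits *complementary* and excludes *alternative*. Sections 2.1 and 2.2 leave the background unstated.

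**4. The diet-deciding factor.** Section 4.7 describes computer-generated random numbers and no stratification. With 55 per group and a proportion p overweight, the 95% range of the chance difference between arms is about ±1.96 × √(2p(1 − p)/55). The protocol does not give p, so a range of assumed values is shown:

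- p = 0.5: 1.96 × √(0.50/55) = 0.187, or ±18.7 percentage points
- p = 0.7: 1.96 × √(0.42/55) = 0.171, or ±17.1 points
- p = 0.9: 1.96 × √(0.18/55) = 0.112, or ±11.2 points

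This is chance imbalance, not bias. How far it would move CAP or LSM cannot be worked out from the protocol.

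**5. Is the factor available?** Section 4.6 places height, weight, waist and BMI at eligibility, at baseline and monthly. Section 5.5 also places them at baseline, and the BMI exclusion in Section 4.3.2 needs them. Table 2, however, marks them at months 1 to 6 only, with nothing at enrolment or allocation. Section 5.2 gives no cut-off for overweight.

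**The case against.** The strongest reply is that the sentence is hedged, offers *complementary* as well, and sits in an ethics paragraph. The hypothesis, endpoints and analysis make no comparison with diet, and Section 5.1 openly says that both groups receive the same care. All of that stands. It makes the correction small, but it does not give *alternative* any support.

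It can also be said that covariates are commonly left to the statistical analysis plan and that randomisation balances overweight status on average. Both are fair. But Section 4.8 already fixes an unadjusted test, and balance on average still leaves the chance differences shown above. Adjustment does nothing for the wording issue, so the two changes have to be justified separately.

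A reader might go further in three ways that the protocol does not support:

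- *Lifestyle treatment starts exactly at baseline, without a lead-in, and so distorts the baseline.* The protocol does not say this. It excludes "A restrictive diet or weight change" of at least 5 kg in the previous 3 months, but not earlier diet or exercise advice, and clinic patients may already have had such advice. Excluding recent dieters and then treating both arms alike is not a contradiction.
- *The diet would explain a null result.* The protocol gives no expected adherence, no conversion from calorie deficit to weight and none from weight to CAP. The restricted diet is individualised and reached over the 6 months. Any projected weight loss would rest on outside assumptions and would still not translate into CAP.
- *The weight change needed to interpret the result would go unreported.* Waist, weight and BMI change to week 24 are already the first secondary endpoint in Section 2.4.

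**Conclusion.** The point holds as a limit on what may be concluded. The trial estimates caffeine added to standard lifestyle care, and *alternative* in Section 6.1 is unsupported by any arm. This rests on the design as written and on no outside figure. A reader might infer that the shared diet and exercise bias the caffeine comparison. They do not: both arms receive them and the tablet is randomised, so the contrast, the planned test and the 55 per group remain valid.

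The adjustment is a modest gain in precision and interpretability. Its value rests on overweight status predicting CAP and LSM change, which is plausible because that status decides who gets calorie restriction, but the protocol does not quantify it. The chance-imbalance range of about 11 to 19 percentage points depends on the assumed share overweight (0.9 down to 0.5).

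**What to change.** 1. Delete *alternative* from the Benefits sentence in Section 6.1.
2. State in the hypothesis (2.1), the primary objective (2.2) and Section 3 that the effect of interest is caffeine added to standard lifestyle care, and limit the conclusions to that.
3. In Section 4.8, replace the unadjusted comparison of CAP and LSM change with a model containing treatment and baseline BMI. Overweight status could be used instead, provided the cut-off that decides who gets the calorie-restricted diet is written down. Say in advance how skewed data will be handled, since the present text chooses between two tests by distribution.
4. Reconcile Table 2 with Sections 4.6 and 5.5 so that the baseline anthropometry is unambiguous.

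The cost is a narrower claim, a few sentences and one extra model term. Care, visits, arms and sample size stay as they are.

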#### **Risks**

There is a risk of participants experiencing side effects of caffeine such as palpitations, high blood pressure, gastrointestinal discomfort, insomnia and anxiety

## 6.2. Obtaining informed Written consent

Informed written consent will be obtained in their preferred language by a medically qualified research assistant. Informed written consent will be taken twice from the volunteer participants. Once for participation in eligibility assessment to check the suitability of the person for the study, and later at the time of enrolling into the study. They will be informed that recruitment to the study will be based on the inclusion and exclusion criteria.

If any changes are made to the study protocol during the study, participants will be informed of such change and possible impact of those changes, and consent will be obtained again

Patients who have expressed willingness to participate in the study will be informed about the study, both verbally and in writing, in their preferred language (English, Sinhalese or Tamil) The information provided will include aims of the study, relevant clinical and laboratory procedures,

28.02.2025

follow up, patient responsibilities, potential benefits to the individual and to society, risks involved and ability to withdraw from the study at any time without giving any reasons.

## **6.3.** Fair participant selection

Fair participant selection will be ensured through objective inclusion criteria, avoiding unjustified exclusions. Randomization balanced key characteristics, minimizing bias.

## 6.4. Protection of rights of participants and provision of medical and psychological support

Participant rights would be protected through strict ethical guidelines. Participation would be entirely voluntary, with individuals informed of their right to refuse or withdraw at any stage without penalty. Informed consent would be obtained. Confidentiality would be maintained, and data handled securely. Additionally, medical and psychological support would be available throughout the study to address any adverse effects or concerns, prioritizing participant well-being and safety.

## 6.5. Volunteer participation and confidentiality

A personal ID number will be allocated to selected volunteers. Names of volunteers will not be used in data collection and report writing. Personal identification data would be stored separately, maintaining strict confidentiality with the chief investigator and used only for the purpose of identification during follow-up if necessary. Personal identity will be disclosed only in the event of a medical emergency or if required by law. Data will be provided to the appropriate health authority in the state hospital in the event of an adverse event when further management is required.

#### Responsibilities of the researchers

Researchers would ensure ethical conduct, participant safety, and protocol adherence.

28.02.2025

## 7. Safety assessment and adverse event (AE) reporting

The study participants will be carefully screened before enrollment in the study regarding their health status and suitability. Inclusion and exclusion criteria have been chosen appropriately to minimize possible risks for volunteers participating in this trial. This will be done by an MBBS and a qualified research assistant trained by the principal investigator. During the study, the volunteers will be closely monitored for safety parameters including AE reporting, physical examination, biochemical, hematology, vital signs measurements, and urinalysis.

The volunteers will be provided with a card stating that they are participating in a clinical study, giving the investigational product, the duration of the study, the address and telephone numbers of the principal investigator. These cards are useful if the study participants consult a physician during their study participation or for emergencies.

The PI and the study team will meet every 4 weeks to review the study procedures, enrollment, screening, implementation, data collection, investigations, and adverse events. The following precautions will be in place to ensure timely detection and identification of adverse reactions and management of such volunteers.

- 1. Participants will be given contact numbers of the PI and another medical investigator who can be reached at any time for reporting or inquiry about any AE or any query related to the study.
- 2. Information on adverse events will be obtained by questioning the participants in general terms such as "How do you feel?" or "How have you been feeling since the last questioning?" or by subjects' spontaneous complaints.
- Medically qualified investigators will obtain appropriate information to determine the
  outcome of the AE and to assess whether it meets the criteria for classification as a
  Suspected Unexpected Serious Adverse Reaction (SUSAR) requiring immediate
  notification..

28.02.2025

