11.	Main ethical issues	Informed consent: Obtained twice (for eligibility and enrollment).  Confidentiality: Participants' personal data will be anonymized.  Risk-benefit balance: Potential side effects of caffeine (e.g., palpitations, insomnia, high blood pressure) will be monitored.  Adverse events reporting: Participants can report symptoms anytime, and serious adverse events will be immediately reported to relevant authorities.

28.02.2025

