#### **Secondary Objectives:**

- To assess changes in liver enzymes (ALT, AST, GGT) with caffeine supplementation.
- To assess the impact on metabolic markers(HbAIC, lipid profile, BMI).
- To assess potential side effects of caffeine supplementation.

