#### 4.6. Data collection:

- Data collection will be done by a two MBBS qualified graduates, who can converse in Sinhala, English and Tamil and are trained by the consultant hepatologist.
- An interviewer administered questionnaire will be used to record basic demographic details of the patient in addition to the data on clinical features. Patient identification data is collected for the purpose of tracing the patient in an adverse event or a medical

28.02.2025

- emergency. However, personal identification will not be used in the database, and the serial numbers will be used instead of names.
- Data collection will be done using a Case Report Form developed by the investigators.
   During each monthly visit, investigators will query regarding any adverse effects. Patients will also undergo clinical examination on visits.

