# 11.10. Annexure 1F

# **Front Label**

# **Participant ID:**

**Random Number:** 

Contents: 60 capsules (200mg each)

**Ingredients:**Caffiene anhydrous

Suggested use: Take two capsules daily after dinner

This recommended dose of this product contains as much caffeine as 4 cups of coffee. Do not consume more than 400 mg of caffeine from any source in a 24 hour period. It may cause nervousness, irritability, sleeplessness and occasional rapid heart rates. In case of accidental overdose, seek professional assistance or contact a poison control center immediately

Storage: Store in a cool, dry place away from sunlight

Warnings: Keep out of reach of children. Do not use if the seal is broken.

Manufactured by: Nutricost

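### Caffeine side effects are a secondary objective, but the symptomatic effects that the protocol names have no fixed CRF item at allocation or follow-up, so their recorded percentages are likely to be incomplete

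*Protocol*

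**What the plan says.** Section 2.2 of the protocol lists among the secondary objectives: "To assess potential side effects of caffeine supplementation". The expected effects are known in advance. Section 6.1 names "palpitations, high blood pressure, gastrointestinal discomfort, insomnia and anxiety". The bottle label in Annexure 1F warns: "It may cause nervousness, irritability, sleeplessness and occasional rapid heart rates". The row on ethical issues in the summary table makes a commitment: "Potential side effects of caffeine (e.g., palpitations, insomnia, high blood pressure) will be monitored".

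Collection is described in three places:
- Section 7, item 2: "Information on adverse events will be obtained by questioning the participants in general terms", with examples that ask how the participant feels now or has felt since last asked, "or by subjects' spontaneous complaints".
- Section 4.6: "During each monthly visit, investigators will query regarding any adverse effects". No list of symptoms is attached.
- Annexure 1C (CRF): one yes/no item on whether any adverse event occurred, followed by degree, relation to treatment, outcome, action taken and a free-text summary. Separately, under History, there is a system review with open headings by body system.

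Sections 4.6 and 5.5 and the CRF also provide for measured blood pressure and heart rate at baseline and every month. Table 2 schedules medical history at enrolment, at allocation and at all six monthly visits.

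For analysis, section 4.8 says that safety outcomes are described, vital signs are given as mean and standard deviation, and a listing of adverse events is presented with the percentage of participants affected. It fixes no test between arms for adverse events.

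**The concern.** How symptoms are asked about, and which fields exist to record them, are settled in the protocol and the CRF. No later analysis plan can recover a symptom that was never asked about. Here the protocol knows which symptoms to look for and makes them an objective, yet relies on the participant to raise them in reply to a general question. Diet, physical activity and alcohol each get a structured questionnaire at every visit. The side-effect objective gets none for its symptomatic part.

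Two consequences follow. First, mild or moderate symptoms that a participant does not think to mention go unrecorded, so the percentages reported for this objective are likely to be too low in both arms. Second, there is no fixed question at allocation. Poor sleep and anxiety can be present before treatment, and an unstructured baseline makes it hard to tell a new or worsened complaint from an old one.

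Section 3 states the aim of showing that the intervention is safe as well as effective, with guidelines in view. A statement on tolerability that rests on non-directed questioning would be weakly supported.

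**Working it through.** **Step 1. Match each named effect to the way it is recorded.**

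| Effect (section 6.1 or label) | Route of recording | Fixed item? |
|---|---|---|
| High blood pressure | Seated measurement, baseline and monthly; CRF field | Yes (measured) |
| Rapid heart rate | Heart rate, baseline and monthly; CRF field | Partly (resting rate at the visit) |
| Palpitations | General question, monthly query, spontaneous complaint, open cardiovascular heading | No |
| Insomnia, sleeplessness | As above, open nervous-system heading at most | No |
| Anxiety, nervousness, irritability | As above, open nervous-system heading at most | No |
| Gastrointestinal discomfort | As above, open gastrointestinal heading | No |

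The gap is confined to the symptomatic effects in the last four rows.

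**Step 2. The number per arm.** Section 4.4 gives SD 5, difference 3, two-sided alpha 0.05, 80% power and 20% dropout. The standard two-sample formula gives 2 × (5 × (1.96 + 0.84) / 3)² = 43.6, so 44 per arm. Allowing for dropout, 44 / (1 − 0.20) = 55 per arm and 110 in total. The stated figure reproduces. It was set for a continuous outcome and not for adverse events.

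**Step 3. Illustration of incomplete capture.** The protocol gives neither adverse event rates nor a capture fraction. Everything in this step is assumed: true rates of 30% on caffeine and 10% on placebo for one symptom, and the same capture fraction c in both arms.

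Recorded rate = c × true rate. Recorded excess = c × (30 − 10) points. Recorded ratio = (c × 30) / (c × 10) = 3 for every c.

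The last column is the chance of a two-sided p < 0.05 with a pooled two-proportion z-test at 55 per arm, by exact enumeration. It serves only as a yardstick, because the protocol plans no such test.

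| Capture c | Recorded, caffeine v placebo | Excess (points) | Expected counts of 55 | z-test power |
|---|---|---|---|---|
| 100% | 30% v 10% | 20 | 16.5 v 5.5 | 0.77 |
| 90% | 27% v 9% | 18 | 14.9 v 5.0 | 0.71 |
| 50% | 15% v 5% | 10 | 8.3 v 2.8 | 0.42 |
| 40% | 12% v 4% | 8 | 6.6 v 2.2 | 0.34 |
| 30% | 9% v 3% | 6 | 5.0 v 1.7 | 0.25 |

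**Step 4. Two limits on this illustration.**
- Sample size is a cause as well. Even full capture gives 0.77 at 55 per arm, and 0.68 at the 44 per arm left after the planned dropout.
- A checklist also draws out unrelated complaints. If it captured 90% and added 10 points of background to each arm (37% v 19%), power would be 0.56. With 20 points added (47% v 29%) it would be 0.50. Both remain above the 0.34 at 40% capture, but the gain is smaller than 0.71 suggests. Asking at allocation and counting only new or worsened symptoms is meant to remove part of that background.

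**The case against.** The strongest reply is that the protocol does more than ask how people feel. Blood pressure, one of the five effects in section 6.1, is measured, and so is heart rate. Investigators ask about adverse effects each month. Medically qualified staff take a history at every visit and have cardiovascular, nervous and gastrointestinal headings in which to write. Participants can telephone at any time, and the label tells both arms which symptoms to expect. Event start and end dates are listed. Non-leading questions are a recognised and coherent method, and nothing in the protocol contradicts their use.

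Much of this stands. Blood pressure falls outside the point, and heart rate largely does. There is a baseline of a kind, so it would be wrong to say that new and old symptoms cannot be separated at all. What remains is that none of these routes puts the same question about sleep, anxiety, palpitations or gut discomfort to every participant, so a blank entry cannot be read as the symptom being absent.

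A reader might go further and infer that all the named effects are under-recorded and that an excess on caffeine will probably be missed. The documents do not support that. They give no rates and no capture fraction. The safety analysis is descriptive, so there is no test to fail. Equal under-capture shrinks the absolute difference and the counts but leaves the ratio between arms unchanged.

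**Conclusion.** The point holds for the symptomatic effects only: palpitations, insomnia, anxiety or nervousness, and gastrointestinal discomfort. They belong to a stated objective and were foreseen by the protocol, yet have no fixed item at allocation or follow-up. The percentages reported for them are likely to be incomplete and hard to distinguish from pre-existing complaints.

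The size cannot be derived from the protocol. On the assumed 30% v 10% and 40% capture, an excess of 20 points would be recorded as 8 (12% v 4%), with the ratio still 3. That rests on assumed rates and on equal capture in both arms. Small numbers would limit the comparison even if every case were recorded. This is a worthwhile and cheap improvement to how the objective is measured. It is not evidence that the safety results would be wrong, and it does not touch the measured vital signs.

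**What to change.** In section 7 and Annexure 1C, keep the open question and ask it first. Follow it with a short checklist of the named symptomatic effects (palpitations; insomnia; anxiety, nervousness or irritability; gastrointestinal discomfort), each answered yes or no and, if yes, with a degree. Use identical wording in both arms, in all three study languages, at allocation and at every monthly visit, and add a row to Table 2.

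In section 4.8, state that the result for the side-effect objective is the number and percentage of participants in each arm with a new or worsened symptom relative to allocation. It should be given symptom by symptom, described and not tested, labelled as solicited, and kept apart from spontaneously reported adverse events. The protocol should also say how a solicited symptom relates to the adverse event definitions used elsewhere in section 7. That is for the investigators to settle.

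The cost is one CRF block and a minute or two at visits that already take place. The downside is that more mild background events will be recorded in both arms.
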